3.2 Subject Compensation

Subjects will accrue compensation according to the below table. They will be handed a \$20 gift card at the end of visit 1. They will accrue \$20 for visit 2 and up to \$300 for visit 3. A check will be mailed via UAMS SAP for their accrued compensation approximately 3-4 weeks after their participation ceases (whether completed or not). If they were to fully attend every visit, their total amount would be \$340. If they stop participating prior to the completion of study visit 3, they will receive prorated pay of \$25 per hour.

Visit	Amount
1	\$20
2	\$20

3	\$300
---	-------

3.3 Recruitment

Potential subjects will be recruited from the Little Rock and central Arkansas areas by use of UAMSHealth social media, word of mouth, the ARResearch.org registry, and contacting prior subjects who indicated they wanted to be contacted about future studies. UAMS students and employees will not be targeted for participation but will not be refused. Study staff will ask enrolled subjects to recruit others if they are comfortable doing so, and study staff will seek subjects within their social circles. Individuals interested in the study will be scheduled for Visit 1.

Facebook Script:

The Center for Translational Research in Aging and Longevity at UAMS is recruiting healthy individuals ages 18-40 for a study about measuring how blood and muscle proteins respond to either a beef patty or vegi-burger(s).

Participants will be compensated for their time. If interested, please contact us:
Email [contact] or call [contact] for more information.

Twitter Script:

Our research team is recruiting individuals ages 18-40 for a study about how blood and muscle proteins respond to a beef patty vs vegi-burger.

Participants will be compensated! Contact us for more info: email [contact], or call [contact]

During the initial conversation (in person or via phone), the following items will be discussed in non-technical language:

- this study is completely voluntary.
- the goal of the study: to see if beef or vege-burgers are more efficient at making proteins in our body.
- the number of visits to UAMS study site and their duration: 2 visits that are less than an hour, and 1 visit that lasts a bit over 10 hours.
- study procedures: must have 2 IV catheters placed and undergo 3 muscle biopsies from one incision on their outer thigh, eat our food for almost 3 full days, fast overnight twice,

have an x-ray for body composition, must get an infusion of stable isotopes (and define what they are).

- risks of procedures: pain, bruising, bleeding, infection, possible fever/chills, discomfort from fasting, small amount of radiation from x-ray, amount of blood taken (approx.. 5 tablespoons), skin numbness and scar formation from biopsy incision.
- compensation for time and travel: up to \$340 if all 3 visits are completed.

ARRResearch.org:

Using the age criteria, study staff will setup the study in the registry. The registry gatekeeper will send the announcement to a predetermined number of registrants (as determined by study staff, e.g. 250 for the initial volley). The submitted language will be emailed to the filtered registrants by the registry's software. Interested registrants (respondents) will click a button to either allow the study staff to contact them via their preferred means or decline to be contacted. If/when a respondent replies to study staff's contact, a brief discussion of the study overview will take place. Respondents who are still interested will schedule visit 1 with study staff. Recruitment metrics will be updated on the registry's website through completion of enrollment.

3.4 Study Registration

This study will be registered on clinicaltrials.gov website as required.

3.5 Sample Storage

Blood samples will be kept frozen at -80 degrees Centigrade or colder once the initial processing has taken place. Samples shall be stored in appropriate freezers in the PI's laboratory, located in a restricted area inside the UAMS IOA building. Said freezers are monitored continuously for proper temperature and working condition. All blood samples shall be identified using a unique study acronym. None of a subject's personal identifiers shall be present on any biological sample.

With explicit permission via the consent form, muscle and plasma samples will be kept indefinitely for future approved uses. No samples will be released to other investigators.

3.6 Randomization

Subjects will be stratified by sex and then randomized equally to one of three groups (one beef patty, one Impossible Burger, or two Impossible Burgers).

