4.0 Study Population

Up to 28 subjects will be enrolled in order to meet the goal of 8 completers in each of the three groups. Attempts will be made to balance sexes within groups.

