7.0 Data Analysis

7.1 Statistical Analysis plan

The post-prandial change in net protein balance (i.e., protein synthesis minus protein breakdown) relative to the baseline in each group will be the primary outcome. Responses of the rates of protein synthesis and breakdown will be secondary outcomes. Additional secondary endpoints will be muscle protein synthesis, plasma EAA and insulin area under the curve above baseline values, and protein kinetics normalized by caloric and EAA intake. Correlation analysis of the relation between protein kinetics and the EAA content of the protein food source will be additional secondary endpoints.

One-way ANCOVA will be used to compare differences in protein kinetics (FSR, NB, PS, and PB) and protein kinetics normalized by caloric and EAA intake. Plasma EAAs and insulin area

under the curve above fasting values will be assessed by a one-way ANOVA. All significant main effects of group will be followed with Bonferroni-adjusted pairwise comparisons. Partial Pearson's correlation coefficients controlling for protein source (beef patty or Impossible Burger) will be used for the correlation analysis. Statistical significance will be accepted at $p < 0.05$.

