7.2 Sample Size Calculation & Power Analysis

A group size of 8 per group was a priori determined based upon an ANCOVA model to compare the protein sources and amounts with respect to mean response of net protein synthesis after adjusting for baseline measures. With this sample size, the ANCOVA model has 80% power to detect effect sizes of $f = 0.484$ or larger. This estimate assumes that the baseline covariate explains 50% of the variation in the response. A 5% α -level will be used to determine statistical significance.

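### Randomisation is stratified by sex but no group comparison names sex; adding it is a cheap gain in power, and in test size where sex is balanced across arms, if sex predicts the response

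*Combined protocol and SAP*

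**What the plan says.** Section 3.6 makes sex the only stratification factor: "Subjects will be stratified by sex and then randomized equally to one of three groups". It gives no block size or other method of restriction. Section 4.0 adds "Attempts will be made to balance sexes within groups" and sets the numbers: "Up to 28 subjects will be enrolled in order to meet the goal of 8 completers in each of the three groups".

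Section 7.1 covers the primary outcome (NB) and the other kinetic outcomes with "One-way ANCOVA will be used to compare differences in protein kinetics (FSR, NB, PS, and PB"), and the same model serves the kinetics normalised by calories and EAA. The plasma EAA and insulin areas "under the curve above fasting values will be assessed by a one-way ANOVA". Group is the only factor in either model. Section 7.1 lists no covariates for the ANCOVA. Section 7.2 supplies the only description, that groups are compared "after adjusting for baseline measures", and adds "This estimate assumes that the baseline covariate explains 50% of the variation in the response". The partial correlations in 7.1 control for protein source only.

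**The concern.** Stratifying by sex, when it works, takes sex differences out of the comparison between arms. A model that omits sex leaves those differences in the error term. If sex predicts the response beyond baseline, two things follow. The standard errors are larger than they need be, which gives up power in a trial with 8 completers per arm. And if sex is closely balanced across arms, the F test rejects less often than its nominal 5% under the null.

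Neither effect is a bias, and neither inflates false positives. Both depend on a sex effect that the documents do not quantify. Servings are fixed in ounces whatever the subject's body size (5.3), which makes a remaining effect plausible but does not establish one. Baseline is already credited with half the variation and may carry part of any sex difference.

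**Working it through.** **Inputs from the documents.** N = 24 (8 per group), f = 0.484, baseline R² = 0.50, alpha = 0.05 (7.1, 7.2); up to 28 enrolled for 24 completers (4.0).

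**Assumed.** s, the share of the post-baseline variance explained by sex, is taken as 0, 10, 20 and 30%. The documents give no value.

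**The plan's own figure.** Noncentrality λ = N f² / (1 − R²) = 24 × 0.484² / 0.5 = 11.24. Error df = 24 − 3 groups − 1 covariate = 20. The noncentral F(2, 20) gives power 80.0%, so the figure in 7.2 reproduces.

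**Adding sex, balanced across arms.** Error df = 19 and λ = 24 × 0.484² / (0.5 × (1 − s)).

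| s | λ | Power with sex |
|---|---|---|
| 0 | 11.24 | 79.7% |
| 10% | 12.49 | 83.9% |
| 20% | 14.06 | 88.1% |
| 30% | 16.06 | 92.1% |

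Break-even with the planned 80.0% is at s of about 0.8%.

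**Simulation, because balance is not guaranteed.** The set-up was 12 men and 12 women (14 and 14 enrolled in the dropout case), equally spaced group means, and the omnibus F test. Three allocations were used: exact balance (4 men and 4 women per arm); blocks of 3 within sex with 28 enrolled and 4 random dropouts; and simple randomisation within sex. There were 60,000 runs per cell for power and 100,000 for type I error.

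| Allocation | Power without sex | Power with sex, s = 0 / 10 / 20 / 30% | Type I error without sex, s = 10 / 20 / 30% |
|---|---|---|---|
| Exact | 78% | 77.6 / 82.0 / 86.4 / 90.8% | 3.6 / 2.4 / 1.5% |
| Blocks of 3, dropouts | 77% | 76.7 / 80.9 / 85.6 / 89.8% | 4.0 / 3.1 / 2.2% |
| Simple | 75% | 72.8 / 77.5 / 81.8 / 86.9% | 4.9 / 4.9 / 5.1% |

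With sex in the model, type I error was 4.9 to 5.1% throughout. Under exact balance, simulated power is about 2 points below the formula because chance imbalance in baseline is included; the gains are similar.

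**Cost and break-even** (150,000 runs per point). If s = 0, adding sex loses about 0.5, 0.9 and 2.5 points of power under the three allocations. It breaks even at s of about 1, 2 and 5.5%.

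**Sensitivity to the sex mix.** With 6 men and 18 women, balanced within sex, type I error without sex is again 3.6 / 2.4 / 1.5%, and power with sex is 77.6 / 81.9 / 86.3 / 90.5%. A 50:50 mix is not needed.

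**Plasma AUC ANOVA** (no covariate, s now a share of the within-group variance, 60,000 runs). Type I error without sex is 3.6 / 2.5 / 1.4% (exact), 3.8 / 2.9 / 2.0% (blocks of 3, dropouts) and nominal (simple). With sex it is 4.9 to 5.2%.

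**The case against.** The strongest reply is that nothing is broken. The estimates are unbiased, the power claim holds for the model that 7.2 describes, and where the test is off-size it errs on the conservative side. The gain depends on a sex effect for which the documents give no figure. The only quantitative account they offer of what drives the response (1.2) is a prediction from EAA content alone, said to explain 80.4% of the variance, with no term for sex or body size. That does not exclude a sex effect within groups, since the 80.4% includes differences between foods, but it is a reason not to presume a large one. This stands, and it is why the point is an improvement and not an error.

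Second, 7.1 does not list its ANCOVA covariates, and one-way limits the factors, not the covariates. The absence of sex from the kinetics models is therefore read from 7.1 and 7.2 together; it is explicit only for the one-way ANOVA of the AUCs. This also stands, and it is itself a reason to name the covariates.

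Third, the test-size argument needs close balance across arms. Under simple randomisation within sex the planned test is nominal, and only the efficiency argument remains, with a higher break-even. That is correct, though unrestricted allocation fits poorly with equal allocation and a target of 8 completers in every group.

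Finally, the figures above are for the omnibus F test. The two hypotheses in section 2.0 are pairwise contrasts, and power for those was not computed.

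**Conclusion.** The concern holds as a low-cost improvement. On the natural reading of 7.1 and 7.2, the one factor used to stratify randomisation is in none of the group models. If sex explains 10 to 20% of the post-baseline variance (an assumption), adding it gains roughly 4 to 8 points of power when sex is balanced across arms, and it restores the test to 5% from 3.6 to 2.4% under exact balance. If sex explains nothing, the loss is 0.3 to 0.5 points with exact balance and about 2.5 points in the least favourable allocation examined. How close the balance will be is unknown: 3.6 states no blocking, 4.0 promises only attempts, and up to four enrolled subjects may not complete. The validity of the planned comparisons and the 80% in 7.2 are not in question.

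**What to change.** In 7.1, specify an ANCOVA with group, sex (the randomisation stratum) and the baseline value for NB, PS, PB, FSR and the kinetics normalised by calories and EAA. Add sex to the group models for plasma EAA and insulin AUC. Base the Bonferroni-adjusted pairwise contrasts on the adjusted means from these models.

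The power figure in 7.2 can stand; a clause saying that it allows for baseline only would keep the two sections consistent.

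The cost is one line of SAP text, no new data, and one error degree of freedom per model (20 to 19 for the kinetics, 21 to 20 for the AUCs). Making the change before results are seen also closes off a later choice about whether to adjust.

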3.7 Muscle Biopsy Procedure

At Visit 3, qualified and credentialed study staff (M.D.) will perform three separate vastus lateralis muscle biopsies of the subject's preferred outer thigh using 1% plain lidocaine for anesthesia. One incision will be used for all 3 biopsies. Approximately 100mg of muscle tissue per biopsy will be obtained using a Bergstrom needle. The tissue will be rinsed with normal saline and flash frozen using liquid nitrogen. The sample will be transferred into a labelled cryo tube and frozen at < -60 degrees C in the PI's lab. Processing and analyses will take place in batches according to the procedures mentioned in 7.3 below.

the incision will be closed with a medical glue, then dressed using a transparent adhesive bandage followed by a 6" wide elastic wrap that will protect the site from incidental contact and assist with hemostasis. Subjects are provided verbal and written instructions for care of the biopsy site, along with the phone number of the study nurse should they have any questions or concerns once leaving the study site.

4.0 Study Population

Up to 28 subjects will be enrolled in order to meet the goal of 8 completers in each of the three groups. Attempts will be made to balance sexes within groups.

4.1 Inclusion Criteria

- Ages 18 – 40 yrs.
- Body Mass Index of 20-32 inclusive.

4.2 Exclusion Criteria

- Unwilling to eat animal proteins
- History of diabetes that requires medication for control of blood glucose

- History of malignancy or chemo/radiation therapy in the 6 months prior to enrollment
- History of gastrointestinal bypass/reduction surgery (Lapband, gastric sleeve, etc.)
- Pregnant females
- Hemoglobin less than 12 g/dL at screening
- Platelets less than 150,000 at screening
- Subjects who cannot refrain from using protein or amino acid supplements for 7 days prior to Visit 3
- Concomitant use of oral or injectable corticosteroids
- Concomitant use of testosterone, IGF-1, or similar anabolic agent
- Any other disease or condition that would place the subject at increased risk of harm if they were to participate, at the discretion of the study physician

5.0 Risks and Benefits

There are no direct benefits for the subjects. Expected risks associated with this protocol are described in detail below. All experimental procedures will be performed by appropriately trained and credentialed personnel.

5.1 Blood sampling:

Blood samples will be collected solely for the purpose of experimentation. The blood will be used to measure plasma amino acid concentrations, stable isotope enrichment, glucose, and insulin. The total amount of blood taken will be approximately 72 mL (~5 tablespoons).

Subjects should have no noticeable effects from this volume.

5.2 DEXA, In Body, ultrasound scans:

The DEXA scan exposes subjects to approximately ½ of the radiation of one chest x-ray.

Subjects will undergo 1 DEXA scan. The In Body and ultrasound scans do not pose any risks.

5.3 Study foods:

The run-in meals are comprised of frozen, ready-to-eat portions that are commercially available at most grocery stores (e.g. Stouffers). The 'test' foods are:

- one 4 ounce (cooked weight) patty of 80/20 beef (from Kroger e.g.)
- one 4 ounce Impossible Burger (<https://impossiblefoods.com/products/burger>)
- two 4 ounce Impossible Burgers

The risk of eating any of these foods is that of a food allergy. Subjects will be shown the list of foods and asked if any of them are intolerable.

5.4 Stable Isotope Infusion:

The primary risks of infusion of the stable isotopes are fever, chills, infection (from contamination). A 0.2 micron in-line filter will be used during the infusion. The isotopes will be purchased from Cambridge Isotope Laboratories (Tewksbury, MA, USA) and sent to the Center for Translational Research in Aging and Longevity at Texas A&M University (College Station, TX) for contractual compounding. Finished products will be shipped to the UAMS Research pharmacist who will store and dispense the isotopes to study staff as needed. Isotopes will be stored in glass vials and frozen until use. Two solutions will be produced: a mixture of L-[ring-²H₅] phenylalanine + U-¹³C₉-¹⁵N tyrosine (for constant infusion IVPB), and a mixture of L-[ring-²H₅] phenylalanine + U-¹³C₉-¹⁵N tyrosine + L-[ring-²H₄] tyrosine (for priming doses IVP).

Isotope rates of infusion:

- L-[ring-²H₅] phenylalanine: priming dose: 3.6µmol/kg. Constant infusion: 3.6 µmol/kg/hour.
- U-¹³C₉-¹⁵N-tyrosine: priming dose: 0.113µmol/kg. Constant infusion: 0.113µmol/kg/hour.
- L-[ring-²H₄] tyrosine: priming dose: 0.31µmol/kg.

IVP vials contain:	IVPB vials contain:
L-[ring- ² H ₅] phenylalanine	L-[ring- ² H ₅] phenylalanine
U- ¹³ C ₉ - ¹⁵ N-tyrosine	U- ¹³ C ₉ - ¹⁵ N-tyrosine
L-[ring- ² H ₄] tyrosine	

5.5 Confidentiality:

A potential risk is the loss of confidentiality. Measures to protect the confidentiality of study participants will be implemented as described in the Data Handling and Record keeping section below.

5.6 Intravenous Catheter insertion:

The risks of inserting an IV catheter are pain, bruising, bleeding, and infection.

5.7 Muscle Biopsy:

The risks of the muscle biopsy procedure include pain, bleeding, bruising, infection, residual numbness from the incision, scar formation, soreness lasting >48 hours, and hematoma.

5.8 Covid-19 Related risks:

Subjects will be COVID-19 negative and/or asymptomatic. Subjects will undergo the current screening procedures in place for UAMS patients at the time of their visits. Visitors will not be permitted unless UAMS policy changes permit them. Subjects will be required to wear a suitable facemask for the entirety of their study visits except when ingesting their meals. Study staff will wear their mandated masks and use universal blood-borne precautions while handling blood samples. Study visit areas are disinfected after study visits as per protocol.

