1.0 Background and Rationale

1.1 Introduction:

According to the USDA Economic Research Service Food Availability Data, beef consumption has been on a general decline for the past 40 years, with current per capita consumption approximately 35% lower in 2020 than in 1980. Some of this decline over the past few years can be attributed to politically motivated claims that carbon emissions from cattle represent a major threat to the global environment. However, the major reason for declining beef consumption is the widely promulgated claim that beef is unhealthy. The hamburger in particular has become a poster child for the notion that beef consumption is responsible for the increasing occurrence of obesity in the United States. The trend of decreasing beef consumption due to perceived health concerns, particularly obesity and associated health problems, has led major fast-food chains such as Burger King and McDonalds, to offer vegetarian burgers as healthy alternatives to the traditional beef burger. However, examination

of the components of the macronutrient matrix of a typical vegetarian burger gives reason to question the health benefits as compared to a traditional beef patty-hamburger.

1.2 Previous research on the topic:

[figure not shown]
One of the principal nutritional benefits of dietary protein in a food source is the stimulation of muscle protein turnover and the net gain of body protein (the anabolic response) (1).

Table 1 shows key aspects of the macronutrient matrix of the Impossible Burger and an 80/20 percent beef patty, with particular emphasis on the protein/essential amino acid (EAA) content.

Table 1. Proposed Experimental Groups			
	80/20 Beef Patty	Impossible Burger	2 Impossible Burgers
Amount (oz)	4 oz	4 oz	8 oz
Protein (g)	19 g	19 g	38 g
EAA (g)	8.9 g	4.2 g	8.4 g
Calories	287	240	480
Calories / g EAA	32	57	57

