The Impossible Burger was chosen as a representative vegetarian burger because soy, which is the highest quality plant-based protein, is the principal protein source (2). Four-ounce servings of a beef patty and of an Impossible Burger each provide 19 g of protein. However, a closer inspection of the macronutrient matrix of the two food sources reveals that the 4 oz beef patty contains more than twice the amount of essential amino acids (EAAs) as compared to a 4 oz Impossible Burger. We recently completed an NCBA-supported study in which the anabolic responses to seven different “ounce equivalents” of protein food sources, as described by the USDA My Plate, were quantified using stable isotope tracers. Rather than being metabolically equivalent, as implied by their designation by My Plate as “ounce equivalent” protein food sources, we found that there was a linear relation between the net gain in body protein and the EAA content of the protein food source (**Figure 1A**) (3). Moreover, the slope of the relation between EAA content and increase in net protein balance was approximately 1, meaning that any difference in EAA content directly corresponded to an equivalent difference in net body protein gain (**Figure 1B**).

These results support the notion that the EAA content of a protein food source is principally responsible for the magnitude of the anabolic response. This fundamental concept is the basis for the scoring of protein quality by the Digestible Indispensable Amino Acid Score (DIAAS) (4). With relevance to the comparison of a beef patty and an Impossible Burger, we found that consumption of 2 ounces of beef resulted in an anabolic response that was approximately 4 g net gain of protein greater than the response to consumption of 2 ounces tofu (Figure 1) (3). The difference in anabolic responses corresponds to the difference in the EAA content of the two protein food sources (Figure 1A). Muscle protein fractional synthesis rate was also greater in those consuming beef as opposed to tofu. Further, compilation of our in-house data set across various populations and food sources indicates that the EAA content of a protein food source explains 80.4% of the variance in the total amount of body protein gained (5). This

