large dataset has allowed us to develop a predictive equation that indicates the total amount of body protein gained will be 7.6 g from 4.2 g of EAA (the Impossible Burger) and 16.5 g from 8.9 g of EAA (beef patty). Stated differently, the greater EAA content of a 4 oz beef patty is predicted to elicit more than double the anabolic response to the same amount of an Impossible Burger.

Plant-based burgers such as the Impossible Burger are being marketed as a one-for-one replacement for beef-based burgers, but the disregard for protein quality is misleading and creates a false perception of equivalent nutritional benefit of the two protein food sources. In

addition to the greater EAA content per gram protein, the profile of EAAs in beef protein more closely reflects the dietary requirements for individual EAAs, as reflected by a DIAAS approximately 40% greater than soy protein. In addition, the overall macronutrient matrix of a protein food source can potentially influence the anabolic response by affecting the temporal EAA response. Both the peak concentration of EAAs after consumption as well as the time to reach the peak concentration affect the anabolic response (5). The Impossible Burger contains various binders and starches that could potentially interfere with the absorption of the EAA from the protein matrix, with a resultant slowing of the rate of absorption and blunting of the maximal concentrations of EAAs in the blood and the speed at which the peak concentrations are reached. These factors likely have a corresponding negative impact on the magnitude of the anabolic response. Since no such issues impede the digestibility of beef protein, it is reasonable to propose that the plasma EAA levels will reach higher peak EAA concentrations, and achieve the peak concentrations more rapidly, than ingestion of the same amount of EAAs in the matrix of the Impossible Burger. As a result of both the advantageous profile of EAAs in beef protein and the more rapid absorption of EAAs, we propose that a beef patty will not only provide a greater anabolic response than an iso-nitrogenous amount of Impossible Burger, but that also consumption of 4 oz of beef patty will also elicit a greater anabolic response than consumption of two Impossible Burgers.

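### Does the missing weight basis for the Impossible Burgers and Table 1 undermine the 19 v 19 g protein and 8.9 v 8.4 g EAA comparisons?

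*Combined protocol and SAP*

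**What the plan says.** Section 5.3 lists the three test foods. Beef is "one 4 ounce (cooked weight) patty of 80/20 beef". The comparator is "one 4 ounce Impossible Burger", and the third arm is two of these. Neither burger entry says raw or cooked.

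In Section 1.2, "Table 1. Proposed Experimental Groups" sets out the same arms at 4, 4 and 8 oz, with 19, 19 and 38 g protein, 8.9, 4.2 and 8.4 g EAA, and 287, 240 and 480 kcal. The text adds: "Four-ounce servings of a beef patty and of an Impossible Burger each provide 19 g of protein". Neither place states a weight basis.

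The rationale in Section 1.2 expects beef to give "a greater anabolic response than an iso-nitrogenous amount of Impossible Burger". In discussing absorption, it expects EAA peaks after beef to be higher and earlier "than ingestion of the same amount of EAAs in the matrix of the Impossible Burger". Section 2.0 words both hypotheses by portion: one 4 oz beef patty against one, and then two, 4 oz Impossible Burgers.

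Section 7.1 makes the post-meal change in net protein balance the primary outcome, and some secondary endpoints divide the kinetics by calorie and EAA intake. Section 7.3 obtains post-meal breakdown by taking exogenous phenylalanine (Phe) away from total Phe appearance. The exogenous part is computed from the protein eaten, its Phe content, a published digestibility and the measured fraction hydroxylated.

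**The concern.** A basis is given for one food and not for its comparator. Cooking changes weight, so 4 oz raw and 4 oz cooked need not hold the same protein. If Table 1 were on one basis and a portion served on another, the first hypothesis would not be an equal-protein contrast, and the small EAA difference behind the second could grow or change sign.

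Food content is also an input to the primary outcome, because exogenous Phe is calculated from the protein eaten and not measured directly. A content figure on the wrong basis in one arm would shift that arm's breakdown, and so its net balance. The fasted baseline has no meal term, so baseline adjustment would not remove the shift.

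**Working it through.** **1. The plan's own figures.** Inputs are from Table 1. Calories per g EAA: 287/8.9 = 32.2, 240/4.2 = 57.1 and 480/8.4 = 57.1, which match the tabulated 32, 57 and 57.

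**2. How sensitive each contrast is, without assuming a cooking yield.**
- One burger: the EAA gap is 8.9 − 4.2 = 4.7 g. To close it, the burger would need 8.9/4.2 = 2.12 times its tabulated EAA.
- Two burgers: the gap is 8.9 − 8.4 = 0.5 g. To close it, they would need 8.9/8.4 = 1.0595 times the tabulated EAA, or 6.0% more.
- Predicted difference in net gain for the two-burger contrast: Section 1.2 says that "the slope of the relation between EAA content and increase in net protein balance was approximately 1", which gives 0.5 × 1 = 0.5 g. Its later prediction equation implies a slope of (16.5 − 7.6)/(8.9 − 4.2) = 8.9/4.7 = 1.89, which gives 0.5 × 1.89 = 0.95 g.

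So only the two-burger contrast is delicate, and Table 1 shows its near-equality openly.

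**3. Do the passages conflict?** Table 1 and Section 5.3 name the same three arms with the same ounces. No food is given two different bases. Read as a description of the groups, which is what its heading says, Table 1 gives the content of the served portions, and the 19 v 19 g and 8.9 v 8.4 g stand.

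**4. Does the second hypothesis need matched EAA?** The sentence about an equal EAA amount concerns absorption for a given amount. It does not mention two burgers or call those arms matched. Section 1.2 rests the two-burger claim on EAA profile and speed of absorption. The arms also differ in protein (19 v 38 g) and calories (287 v 480), so EAA amount was never the only difference.

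**5. Route to the primary outcome.** Net balance = synthesis − (total Phe appearance − exogenous Phe). If synthesis is computed without the exogenous term (an assumption, since the model is deferred to a cited source), an error in exogenous Phe passes to net balance one for one in Phe units. It arises only if the protein entered is not the protein eaten, and Section 7.3 specifies the latter. The documents give no Phe content for either food, so its size cannot be computed from them.

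**6. Route to the EAA correlation.** Section 7.1 controls for protein source. Within beef the tabulated EAA is constant, so its residual is 0. Within the burger arms the mean is (4.2 + 8.4)/2 = 6.3 g and the residuals are −2.1 and +2.1 g. A different weight basis multiplies both burger values by one constant, which leaves a correlation unchanged. This holds for given kinetics and fully eaten portions.

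**7. Sample size.** Inputs from Section 7.2: N = 3 × 8 = 24, f = 0.484, R² = 0.5, alpha 0.05. Noncentrality = 24 × 0.484²/(1 − 0.5) = 11.24. With 2 and 20 degrees of freedom the power is 0.800, as stated. Food content does not enter.

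**The case for a change.** The strongest case is that a mismatch is plausible. Take 4 and 9 kcal per g for protein and fat, and read 80/20 as 20% fat by raw weight; the documents give none of these. Four ounces is 113.4 g, so fat is 0.20 × 113.4 = 22.7 g, and 22.7 × 9 + 19 × 4 = 280 kcal, close to the tabulated 287. That is compatible with a beef column on raw weight, while Section 5.3 serves cooked weight. With assumed yields of 65 to 90% and full protein retention, a mismatch in one food would put the two-burger EAA gap anywhere from 8.9 − 8.4/0.65 = −4.0 g to 8.9/0.65 − 8.4 = +5.3 g, depending on which food is affected.

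This stands as a reason for care when content figures are entered. It does not show a mismatch: the documents do not give the fat share of a cooked patty, so the calorie check cannot separate raw from cooked. The yields are assumed and applied alike to two different foods.

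It is also true that no composition source is named for beef. For the burger, Section 5.3 gives a manufacturer product link, whose content cannot be checked here. Sections 7.1 and 7.3 nevertheless fix the quantity needed, namely what was eaten, and converting a weighed portion on its own basis is ordinary analytic practice.

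**Conclusion.** No change to the plan is needed. This is a labelling gap of the kind analysts fill sensibly: the basis is stated for beef only, nothing contradicts it, and the effect is nil if Table 1 describes the food served. The part that survives is small. The tabulated two-burger EAA gap is 0.5 g and would close with 6.0% more EAA in the burgers, so the rationale for that contrast should not be read as resting on a secure EAA advantage. The one-burger gap of 4.7 g is not delicate in that sense.

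The arms, hypotheses, primary outcome and sample size are the same on any basis, and no computational error in net balance is shown. This conclusion assumes that content is entered for the portion actually eaten, as Sections 7.1 and 7.3 say. If the bases proved to differ, the equal-protein description in the rationale would need qualifying when results are reported, but the portion-based hypotheses would still be tested as written. No view is taken on which portion or basis is right.
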